#### 201215

Chemistry (liver function, blood glucose, creatine phosphokinase)	$\checkmark$		$\checkmark$													
Pregnancy test9	$\checkmark$	$\checkmark$		$\checkmark$	$\checkmark$		$\checkmark$			$\checkmark$	$\checkmark$		$\checkmark$	$\checkmark$		
HCV/HDV/HIV	$\checkmark$															
ANA	$\checkmark$															
B-ultrasound 	$\checkmark$			$\checkmark$				$\checkmark$				$\checkmark$		$\checkmark$		$\checkmark$
AFP				$\checkmark$				$\checkmark$		$\checkmark$		$\checkmark$		$\checkmark$		
Urinalysis 	$\checkmark$	$\checkmark$	$\checkmark$	$\checkmark$	$\checkmark$		$\checkmark$		$\checkmark$	$\checkmark$	$\checkmark$		$\checkmark$	$\checkmark$		$\checkmark$
Electrolytes (Sodium, potassium, chloridum, phosphorus and calcium)	$\checkmark$		$\checkmark$													
International Normalized Ratio(INR)	$\checkmark$	$\checkmark$		$\checkmark$												
Renal function(Blood Creatinine clearance, blood urea nitrogen and blood uric acid)	$\checkmark$		$\checkmark$													
HBV DNA 	$\checkmark$	$\checkmark$		$\checkmark$	$\checkmark$	$\checkmark$	$\checkmark$	$\checkmark$		$\checkmark$	$\checkmark$	$\checkmark$	$\checkmark$	$\checkmark$		
HBeAg/Anti-HBe	$\checkmark$	$\checkmark$		$\checkmark$												
HBsAg/Anti-HBs		$\checkmark$														
Resistance surveillance 		$\checkmark$														
Investigational product																
Study drug dispensed and reconciliation of drug dupply 		$\checkmark$		$\checkmark$												
Serum and plasma storage	$\checkmark$															

#### 201215

- 1 All results to be obtained before baseline visit.
- 2 No more than 6 days before or 6 days after the date scheduled based on the time from baseline visit not from the previous visit.
- 3 Demographic data includes birth date, gender and race
- 4 Medical history will include any acute and chronic medical conditions including prior surgery, information related to hepatitis B history, any current and prior HBV medications, and previous HBV-related procedures.
- 5 Update any new medical conditions and/or concomitant medications that have occurred since study screening.
- 6 Concomitant medications including traditional Chinese medicines and/or herbal remedies.
- 7 At screening, a complete physical examination will be performed. For all following indicated visits, a brief physical examination will be performed.
- 8 Including blood pressure, pulse, respiratory rate and temperature.
- 9 Urine pregnancy test will be performed at screening, baseline and every 3 months after dosing.
- 10 Tests will be performed at central lab.
- 11 B ultrasound examination include liver, pancreas, spleen, gall bladder and kidney.
- 12 Urinalysis: urine glucose, ketones, specific gravity, blood, pH and protein.
- 13 HBV DNA will be tested using Roche COBAS Taqman HBV test (LLD:20IU/ML).
- 14 Resistance surveillance will be performed at baseline or under the condition defined in protocol by direct sequencing of the polymerase gene. See Section 6.2.5
- 15 Each study visit: All study medication to be collected and reconciled.

## 6.1. Critical Baseline Assessments

Subjects will be screened within 4 weeks prior to enrolment to determine eligibility for participation in the study. The assessments to be performed are listed in Table 1.

Prior to dispensing study medication on Day 1, the procedures listed in Table 1 must be performed and documented in the CRF.

The first dose of study medication will be administered at this visit, after all the study procedures have been completed. Subjects can be discharged immediately after dosing.

## 6.2. Efficacy

Samples for efficacy analysis will be collected at times outlined in Table 1. Collection and processing procedures for each type of sample will be detailed in the SPM.

## 6.2.1. Serum/Plasma Storage

Serum and plasma will be stored at the central laboratory and frozen at or below -20°C to allow possible evaluation of changes in laboratory markers of HBV infection (including resistance testing) observed during the course of the study.

## 6.2.2. Virological Endpoint

To evaluate the proportion of subjects with HBV DNA< 20 IU/mL at week 48,96 ,144 and viral load change over time, HBV DNA level will be quantified using the sensitive HBV test in central lab at times outlined in Table 1.

### 6.2.3. Biochemical Endpoint

To evaluate the ALT normalization at week 48, 96 and 144, ALT will be measured at times outlined in Table 1.

### 6.2.4. Serological Endpoint

To evaluate the serological response at week 48, 96 and 144, HBeAg/anti-HBe and HBsAg/anti-HBs will be measured at times outlined in Table 1.

### 6.2.5. Resistance Surveillance

Resistance surveillance including genotypic analysis of the HBV polymerase gene will be performed on stored serum by direct sequencing using a central laboratory in the following situations:

- All subjects at baseline.
- Subjects that do not achieve satisfied response to TDF(see section 3.1)
- Subjects remain HBV DNA detectable at week 48, 96, or their last visit in the study.

## 6.3. Safety

#### 6.3.1. On-Treatment ALT Flare, ALT Elevation With or Without Hepatic Dysfunction, and Post-Treatment Exacerbation of Hepatitis Management

DEFINITIONS

ALT FLARE	ALT Both >2x baseline value and >10x ULN	See Section 6.3.1.1
ALT ELEVATION With HEPATIC DYSFUNCTION	ALT Both >2x nadir value and >5xULN with evidence of worsened hepatic function (e.g. Direct Bilirubin >1.5mg/dL INR ≥ 1.7, or abnormal serum albumin ≤2.7)	See Section 6.3.1.1
ALT ELEVATION ALONE	ALT Both >2x nadir value and >5x ULN	See Section 6.3.1.2

#### 6.3.1.1. Management of ALT Flare or ALT Elevation With Hepatic Dysfunction in Subjects Receiving Study Medication

If laboratory results indicate **ALT Flare** or **ALT Elevation With Hepatic Dysfunction** the following is recommended:

Schedule the subject to return to the clinic as soon as possible (ideally within 3 days after initial laboratory results were drawn). During the visit, a clinical assessment of the subject will be performed. The assessment should include a physical examination and evaluation of the subject's mental status.

Check the following laboratory parameters: serum ALT and AST, alkaline phosphatase, total and direct bilirubin, INR, and serum albumin.

□□If the ALT Flare or ALT Elevation With Hepatic Dysfunction is confirmed, request the clinical laboratory to conduct reflex testing for plasma HBV DNA, serology for HBV (HBsAg, HBeAg, HBeAb, and HBsAb), HDV, HAV IgM, HCV, and HEV

Based on the results of the confirmatory tests, the following treatment modifications are recommended:

#### Evidence of worsening HBV infection:

• If Plasma HBV DNA is increasing (≥1 log increase), the investigator should discuss initiation of additional therapy with the medical monitor.

2013N184141 00

#### In the absence of evidence of worsening HBV infection:

- If ALT levels are elevated (+/- direct bilirubin/INR/albumin) as above, the subject may remain on study medication and should be monitored with ALT and AST, alkaline phosphatase, total and direct bilirubin, INR, and serum albumin at least weekly until laboratory abnormalities return to baseline level.
- During monitoring, if the ALT values (+/- direct bilirubin/INR/albumin) are worsening or remain persistently abnormal or elevated after 4weeks, the Investigator should discuss with the Medical Monitor regarding the monitoring schedule and whether the study drug should be discontinued.

For subjects with bridging fibrosis or cirrhosis, study drug discontinuation with treatment-free follow-up is to be avoided due to the potential risk of exacerbation of hepatitis in the setting of low hepatic reserve which could lead to decompensation. Subjects with bridging fibrosis or cirrhosis should be placed on commercially available HBV therapy following study drug discontinuation.

Subjects should be followed until laboratory parameters return to baseline up to a maximum of 6 months after the initial occurrence of the event.

#### 6.3.1.2. Increased monitoring for On-Treatment ALT Elevation Alone

In patients with confirmed ALT Elevation Alone (both >2x nadir and also >5xULN) but have not reached ALT Flare (Both ALT >2x baseline value and >10x ULN) and do not have evidence of worsened hepatic function (e.g. Direct Bilirubin >1.5mg/dL INR ≥1.7, or abnormal serum albumin <=2.7) the subject may remain on study medication and should be monitored weekly until ALT levels return to baseline level. During monitoring, if after 4 weeks the ALT values remain stable but persistently abnormal, the Investigator should discuss with the Medical Monitor regarding the monitoring schedule.

If patients worsen to reach ALT Flare definition or ALT Elevation with hepatic dysfunction, manage as above in Section 6.3.1.1.

Subjects should be followed until laboratory parameters return to baseline up to a maximum of 6 months after the initial occurrence of the event.

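### Weekly monitoring for ALT Elevation Alone starts on a nadir and ULN trigger but stops at baseline, so a confirmed rebound in a subject with baseline ALT above 5x ULN can already meet the stop rule

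*Protocol*

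**What the plan says.** Protocol section 6.3.1.2 applies to "confirmed ALT Elevation Alone (both >2x nadir and also >5xULN"), provided the subject has neither an ALT flare (above twice baseline and above 10x ULN) nor worsened hepatic function. For such a subject it says "the subject may remain on study medication and should be monitored weekly until ALT levels return to baseline level".

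Two further steps follow in the same section:

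- A discussion of the schedule with the Medical Monitor: "During monitoring, if after 4 weeks the ALT values remain stable but persistently abnormal".
- Event follow-up: "Subjects should be followed until laboratory parameters return to baseline up to a maximum of 6 months".

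For ALT elevation with hepatic dysfunction, the definitions table in section 6.3.1 uses the same ALT trigger: "ALT Both >2x nadir value and >5xULN with evidence of worsened hepatic function". Where HBV infection is not worsening, section 6.3.1.1 then asks for monitoring "at least weekly until laboratory abnormalities return to baseline level".

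Protocol section 4.3, criterion 4, excludes only screening ALT above 10x ULN. SAP section 6.1 defines baseline as the last assessment before the first dose. Routine assessments, including liver function, are every 12 weeks (Protocol section 3.1).

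**The concern.** The start and stop rules use different reference points. A subject who enters with ALT above 5x ULN, improves on treatment and then rebounds can meet the trigger while still at or below the pre-treatment value. Read literally, weekly monitoring is then over as soon as it begins. The 4-week discussion applies only while monitoring is running, and the follow-up also ends at baseline, so neither is clearly required.

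For these subjects little else in section 6.3.1 covers the rebound. A flare requires ALT above twice baseline as well as above 10x ULN. That means above 16x ULN for a baseline of 8x, and above 20x for a baseline of 10x. Below that level and without hepatic dysfunction, Elevation Alone is the only ALT category that applies. The repeat HBV DNA and serology in section 6.3.1.1 are not part of section 6.3.1.2.

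**Working it through.** The plan states no figure on this point, so the check is of the threshold logic and then of the length of the gap.

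**Inputs** (ALT in multiples of ULN): baseline *b*, nadir *n*, current confirmed ALT *a*.

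- Start (6.3.1 and 6.3.1.2): *a* > 2*n* and *a* > 5.
- Flare, which is excluded from this category: *a* > 2*b* and *a* > 10.
- Literal stop (6.3.1.2): *a* ≤ *b*.
- Entry limit (4.3, criterion 4): screening ALT at most 10. The table below takes baseline in the same range.

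**When start and stop hold together.** Both are met when max(5, 2*n*) < *a* ≤ *b*. Such a value exists only if *b* > 5 and *n* < *b*/2. It is never a flare, because *a* ≤ *b* rules out *a* > 2*b*.

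**Example.** Take *b* = 8, *n* = 1, *a* = 6. Then 6 > 2 and 6 > 5, so monitoring starts. Since 6 is not above 16, it is not a flare. Since 6 ≤ 8, the stop rule is already met.

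**Conflict band** (above the lower figure, up to and including the upper):

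| Nadir | *b* ≤ 5 | *b* = 6 | *b* = 8 | *b* = 10 |
|---|---|---|---|---|
| ≤ 2.5 | none | 5–6 | 5–8 | 5–10 |
| 3 | none | none | 6–8 | 6–10 |
| 4 | none | none | none | 8–10 |

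**Length of the gap.** If weekly tests are not required, the next required ALT is at the next scheduled visit. Section 6.3.1.2 gives no interval for confirming the elevation. The only one given for ALT events on treatment is the target in section 6.3.1.1, "ideally within 3 days after initial laboratory results were drawn". I therefore assume confirmation *d* = 0 to 28 days after a scheduled visit.

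Visits are 12 × 7 = 84 days apart. Table 1, footnote 2 allows "No more than 6 days before or 6 days after the date scheduled based on the time from baseline visit", so spacing runs from 84 − 12 = 72 to 84 + 12 = 96 days. The gap is spacing minus *d*. Tests not required are the number of whole weeks *k* ≥ 1 with 7*k* < gap.

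| Spacing (days) | *d* = 0 | *d* = 3 | *d* = 7 | *d* = 14 | *d* = 28 |
|---|---|---|---|---|---|
| 72 | 72 d, 10 tests | 69 d, 9 | 65 d, 9 | 58 d, 8 | 44 d, 6 |
| 84 | 84 d, 11 | 81 d, 11 | 77 d, 10 | 70 d, 9 | 56 d, 7 |
| 96 | 96 d, 13 | 93 d, 13 | 89 d, 12 | 82 d, 11 | 68 d, 9 |

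**The other two categories.** Elevation with hepatic dysfunction has the same mismatch in its ALT part. It matters less there, because the other laboratory abnormalities must also return to baseline. A flare has no mismatch, because its own trigger requires ALT above twice baseline.

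**Effect of the proposed stop rule** (*a* ≤ *b* and trigger no longer met). The overlap disappears by construction. If *b* ≤ 5, then *a* ≤ *b* implies *a* ≤ 5. If *n* ≥ *b*/2, then *a* ≤ *b* implies *a* ≤ 2*n*. In both cases the old and new rules coincide. I also ran a grid (*b* from 1 to 10, *n* from 0.25 to 5.75 with *n* ≤ *b*, *a* from 0.25 to 20, steps of 0.25, flares removed). It gives 2,715 points meeting start and stop together under the current rule and 0 under the proposed one. Where *b* ≤ 5 or *n* ≥ *b*/2, the two rules differ at 0 points.

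**The case against.** The best reply is that returning to a level presupposes being above it. A reading that stops monitoring on the day it starts makes the instruction void, and the 4-week step shows that monitoring was meant to continue. This is a fair account of the intent. It does not repair the rule: on that reading an affected subject has no ALT value at which weekly checks end. The 4-week discussion and the 6-month maximum limit the process, but neither is an ALT threshold.

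Several other points stand:

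- Section 6.3.1 does not define baseline. Using the SAP definition for clinical management is the natural choice, but it is an assumption.
- The wording is permissive and nothing prevents extra tests, so the counts above are tests not required rather than tests that would be missed.
- The affected group is narrow and may be empty. The documents give no baseline ALT distribution or rebound rate.
- Twelve-weekly chemistry, central HBV DNA, the breakthrough rule and escalation to section 6.3.1.1 all continue.
- No text states that the nadir trigger is meant to catch rebounds. That is inferred from its form.
- The fix is limited: with baseline 8x and nadir 1x it would still end monitoring at 4.9x ULN. It removes the contradiction between the two rules and does not try to set an ideal stopping level.

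**Conclusion.** The concern holds, as a minor point of safety monitoring. For a subject with baseline ALT above 5x ULN whose nadir is below half of baseline, a confirmed rebound above both 5x ULN and twice nadir but not above baseline meets the start and stop rules together.

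On the literal reading, the gap to the next required ALT is 56 to 84 days at nominal visit spacing, and 44 to 96 days across the visit windows. This rests on the pre-dose definition of baseline and on the assumed confirmation delay of 0 to 28 days. The threshold conflict itself is certain. How often it would occur, and whether sites would act on the literal wording, cannot be judged from the documents. The primary endpoint is not affected.

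**What to change.** In Protocol section 6.3.1.2, end both the weekly monitoring and the event follow-up when ALT is at or below baseline **and** no longer meets the trigger, that is, ALT ≤ 5x ULN or ≤ 2x nadir. Keep the 6-month maximum. The same phrase could be added to the ALT part of section 6.3.1.1 for consistency.

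The cost is one wording change and some extra ALT samples in affected subjects only. Six months holds about 26 weekly tests, of which 2 fall on scheduled visits, so the ceiling is about 26 − 2 = 24 extra samples per event.

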# 6.3.1.3. Management of Exacerbation of Hepatitis in Subjects who have Discontinued Study Medication

If laboratory results indicate **ALT Flare** or **ALT Elevation With Hepatic Dysfunction** and the subject is on no post-study therapy for HBV, the following is recommended:

- Schedule the subject to return to the clinic as soon as possible (ideally no later than 3 days after the initial laboratory values were drawn). During the visit, perform a clinical assessment of the subject.
- Check the following laboratory parameters: serum ALT and AST, alkaline phosphatase, total and direct bilirubin, INR, and albumin.
- If the ALT Flare or ALT Elevation With Hepatic Dysfunction is confirmed, request the clinical laboratory to conduct reflex testing for plasma HBV DNA, serology for HBV (HBsAg, HBeAg, HBeAb, and HBsAb), HDV, HAV IgM and HCV. If Plasma HBV DNA is increasing (≥1 log increase), the investigator should consider immediate initiation of approved therapy.
- Subjects should be followed until laboratory parameters return to baseline up to a maximum of 6 months after the initial occurrence of the event.

Please refer to Appendix 2 for the recommend method for managing lactic acidosis

#### 6.3.2. Adverse Events

The investigator or site staff will be responsible for detecting, documenting and reporting events that meet the definition of an AE or SAE.

#### 6.3.2.1. Definition of an AE

Any untoward medical occurrence in a patient or clinical investigation subject, temporally associated with the use of a medicinal product, whether or not considered related to the medicinal product.

Note: An AE can therefore be any unfavorable and unintended sign (including an abnormal laboratory finding), symptom, or disease (new or exacerbated) temporally associated with the use of a medicinal product. For marketed medicinal products, this also includes failure to produce expected benefits (i.e., lack of efficacy), abuse or misuse.

Events meeting the definition of an AE include:

- Exacerbation of a chronic or intermittent pre-existing condition including either an increase in frequency and/or intensity of the condition
- New conditions detected or diagnosed after study treatment administration even though it may have been present prior to the start of the study
- Signs, symptoms, or the clinical sequelae of a suspected interaction
- Signs, symptoms, or the clinical sequelae of a suspected overdose of either study treatment or a concomitant medication (overdose per se will not be reported as an AE/SAE) unless this is an intentional overdose taken with possible suicidal/self-harming intent. This should be reported regardless of sequelae.

"Lack of efficacy" or "failure of expected pharmacological action" per se will not be reported as an AE or SAE. However, the signs and symptoms and/or clinical sequelae resulting from lack of efficacy will be reported if they fulfil the definition of an AE or SAE.

The signs and symptoms and/or clinical sequelae resulting from lack of efficacy will be reported if they fulfill the definition of an AE or SAE. Also, "lack of efficacy" or "failure of expected pharmacological action" also constitutes an AE or SAE.

Events that **do not** meet the definition of an AE include:

- Medical or surgical procedure (e.g., endoscopy, appendectomy); the condition that leads to the procedure is an AE
- Situations where an untoward medical occurrence did not occur (social and/or convenience admission to a hospital)
- Anticipated day-to-day fluctuations of pre-existing disease(s) or condition(s) present or detected at the start of the study that do not worsen
- The disease/disorder being studied, or expected progression, signs, or symptoms of the disease/disorder being studied, unless more severe than expected for the subject's condition

#### 6.3.2.2. Definition of an SAE

A serious adverse event is any untoward medical occurrence that, at any dose:

- a. Results in death
- b. Is life-threatening

NOTE: The term 'life-threatening' in the definition of 'serious' refers to an event in which the subject was at risk of death at the time of the event. It does not refer to an event, which hypothetically might have caused death, if it were more severe.

c. Requires hospitalisation or prolongation of existing hospitalisation

NOTE: In general, hospitalisation signifies that the subject has been detained (usually involving at least an overnight stay) at the hospital or emergency ward for observation and/or treatment that would not have been appropriate in the physician's office or out-patient setting. Complications that occur during hospitalisation are AEs. If a complication prolongs hospitalisation or fulfills any other serious criteria, the event is serious. When in doubt as to whether "hospitalisation" occurred or was necessary, the AE should be considered serious.

Hospitalisation for elective treatment of a pre-existing condition that did not worsen from baseline is not considered an AE

d. Results in disability/incapacity, or

NOTE: The term disability means a substantial disruption of a person's ability to conduct normal life functions. This definition is not intended to include experiences of relatively minor medical significance such as uncomplicated headache, nausea, vomiting, diarrhea, influenza, and accidental trauma (e.g. sprained ankle) which may interfere or prevent everyday life functions but do not constitute a substantial disruption.

- e. Is a congenital anomaly/birth defect
- f. Medical or scientific judgment should be exercised in deciding whether reporting is appropriate in other situations, such as important medical events that may not be immediately life-threatening or result in death or hospitalisation but may jeopardise the subject or may require medical or surgical intervention to prevent one of the other outcomes listed in the above definition. These should also be considered serious. Examples of such events are invasive or malignant cancers, intensive treatment in an emergency room or at home for allergic bronchospasm, blood dyscrasias or convulsions that do not result in hospitalisation, or development of drug dependency or drug abuse.

#### 6.3.2.3. Sentinel Events

A Sentinel Event is a GSK-defined SAE that is not necessarily drug-related but has been associated historically with adverse reactions for other drugs and is therefore worthy of heightened pharmacovigilance. Medical monitor review of all SAEs for possible Sentinel Events is mandated at GSK. The GSK medical monitor may request additional clinical information on an urgent basis if a possible Sentinel Event is identified on SAE review. The current GSK-defined Sentinel Events are listed below:

- Acquired Long QT Syndrome
- Agranulocytosis/Severe Neutropenia
- Anaphylaxis & Anaphylactoid Reactions
- Hepatotoxicity
- Acute Renal Failure
- Seizure
- Stevens Johnson syndrome/Toxic epidermal necrosis

#### 6.3.3. Laboratory and Other Safety Assessment Abnormalities Reported as AEs and SAEs

Any abnormal laboratory test results (hematology, clinical chemistry, or urinalysis) or other safety assessments (e.g., ECGs, radiological scans, vital signs measurements), including those that worsen from baseline, and felt to be clinically significant in the medical and scientific judgement of the investigator are to be recorded as AEs or SAEs. However, any clinically significant safety assessments that are associated with the underlying disease, unless judged by the investigator to be more severe than expected for the subject's condition, are not to be reported as AEs or SAEs.

